#### 4.3.8 Visit Windows

The protocol-specified in-clinic visit windows are  $\pm$  7 days during the Randomization Phase, however, analysis windows will be continuous to include all data. Refer to Appendix 1 for details on the expected evaluation intervals for the details on the schedule of assessments during the Randomization and Extension Phases. The data portal contains a report where all visits and their acceptable windows will be projected at the baseline visit. The baseline visit for the randomization phase is expected to be the date of randomization and first dose of randomized treatment.

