#### **On-Treatment Analysis Windows**

# Table 1:Analysis Windows for Efficacy Parameters: ADAS-cog and CDR in
the 48 week Randomization Phase

Evaluation	Protocol-Specified Day	Analysis-Specified Interval
Randomization Phase		
Week 12	Day 84	Day 2-126
Week 24	Day 168	Day 127-210
Week 36	Day 252	Day 211-294
Week 48	Day 336	Day 295-420

Note: Baseline assessment will be defined as the last available assessment on or before first day of randomization phase study drug [For CDR the window for baseline assessment will be extended to include assessments up to and including Day 2 of study drug as one subject completed the CDR after starting study treatment. This assessment was felt to still be a valid baseline assessment due to the limited treatment at the time of assessment. The Week 12 window will be adjusted accordingly to Day 3-126.]. Days based on days from first day of randomization phase study drug.

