# Table 2:Analysis Windows for All Other Efficacy Parameters Including NPI,
ADCS-ADL, MMSE, MoCA, Volumetric MRI, CSF Biomarkers and
Blood Biomarkers and NACC measures in the 48 week
Randomization Phase.

Evaluation	Protocol-Specified Day	Analysis-Specified Interval
Randomization Phase		
Week 24	Day 168	Day 2-252
Week 48	Day 336	Day 253-420

Note: Baseline assessment will be defined as the last available assessment on or before first day of randomization phase study drug. Days based on days from first day of randomization phase study drug.

Table 3:	Analysis Windows for Safety Parameters: Sheehan Suicidal
	Tracking, Vital Signs, Lab Assessments, PK and ECG

Evaluation	Protocol-Specified Day	Analysis-Specified Interval
Randomization Phase		
Week 4	Day 28	Day 2-42
Week 8	Day 56	Day 43-70
Week 12	Day 84	Day 71-98
Week 16	Day 112	Day 99-126
Week 20	Day 140	Day 127-154
Week 24	Day 168	Day 155-182
Week 28	Day 196	Day 183-210
Week 32	Day 224	Day 211-238
Week 36	Day 252	Day 239-266
Week 40	Day 280	Day 267-294
Week 44	Day 308	Day 295-322
Week 48	Day 336	Day 323-420

Note: Baseline assessment will be defined as the last available assessment on or before first day of randomization phase study drug. Days based on days from first day of randomization phase study drug.

If a participant has more than one record within an analysis window, the latest record within the window will be used in the analysis.

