#### 4.4 Analysis Periods and Study Phases

Analysis periods and study phases are defined as follows:

- Screening Phase: will include all assessments on or before the first day of study drug.
- On-Treatment in Randomization Phase (Safety Assessments): except where indicated, "ontreatment" in the Randomization Phase will include all assessments after first day of study drug and up to the first day of dosing of the Open Label Extension Phase study drug (for subjects entering extension) or up to the last day of Randomization Phase study drug + 30 days, whichever comes first. For AEs, "on-treatment" in the Randomization Phase will include first day of dosing of the Randomization Phase study drug up to the last day of Randomization Phase study drug + 30 days for those not going into the Extension Phase or up to the day before the first day of dosing of Extension Phase medication for those subjects who do.
- On-Treatment in Randomization Phase (Efficacy Assessments): except where indicated, "on-treatment" in the Randomization Phase will include all assessments after first day of study drug and up to the first day of dosing of the Open Label Extension Phase study drug (for subjects entering extension) or up to the last day of Randomization Phase study drug + 3 days, whichever comes first.
- On-Treatment in Open Label Extension Phase (Safety Assessments): except where indicated, "on-treatment" in the Open Label Extension Phase will include all assessments after first day of open label study drug and up to the last day of Open Label Extension Phase study drug + 30 days. For AEs, "on-treatment" in the Open Label Extension Phase will include first day of dosing of the Open Label Extension Phase study drug up to the last day of Open Label Extension Phase study drug up to the last day of Open Label Extension Phase study drug + 30 days.
- On-Treatment in Open Label Extension Phase (Efficacy Assessments): will include all efficacy assessments after the first day of dosing of OL Extension Phase study drug to the

last day of study drug +3 days. Baseline for the extension will be the last available assessment on or before the first day of dosing of OL Extension Phase medication.

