#### 4.10.3 Laboratory Data

Clinical laboratory evaluations include:

- Hematology: hemoglobin, hematocrit, platelets, complete blood count with differential and absolute neutrophil count
- Serum Chemistry: sodium, potassium, chloride, calcium, ALT, AST, LDH, alkaline phosphatase, GGT, phosphorous, bicarbonate, CPK, total protein, albumin, direct bilirubin, indirect bilirubin, total bilirubin, glucose, creatinine, BUN, uric acid, total cholesterol, LDL, HDL, triglycerides
- Urinalysis: pH, specific gravity, protein, glucose, ketones, urobilinogen, bilirubin, blood

Clinical laboratory values will be expressed using conventional (US) and standard international (SI) units. In the event of repeat values within the same analysis visit, if any measurement has abnormal results, that measurement will be used for presentation in by-visit tables. If none of the measurements are abnormal, or all of them are abnormal, the worst measurement in the analysis

visit interval will be used for presentation in by-visit tables. All measurements will be presented in listings and considered for evaluation of potential drug- induced liver injury (DILI) or abnormalities.

Due to the COVID-19 pandemic crisis some sites might utilize local laboratories for some visits. These local laboratory values will be combined with the centralized laboratory values by normalizing them to the central laboratory using methods described in Chuang-Stein 1992

On-treatment laboratory abnormalities are those with an assessment date after the date/time of first dose of study drug and within 30 days after the last dose of study drug. For the Randomization Phase, treatment-emergent laboratory abnormalities will be assessed from the date of first dose of study drug until: 1) the first day of the Extension Phase or 2) if the subject did not continue into the Extension Phase, 30 days after the last dose of study drug. For the Extension Phase, treatment-emergent lab abnormalities will be assessed from the first dose during the Extension Phase until 30 days after the last dose of study drug. (See section 4.3)

The observed value and change from baseline will be summarized for each continuous laboratory parameter for the Randomization and Extension Phases, separately, in both conventional and SI units.

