#### 4.10.5 Vital Signs and Physical Measurements

The observed value and change from baseline in vital signs and physical measurements will be summarized for each arm at each visit for the Randomization and Extension Phases, separately. The summary will be based on the "on-treatment" data after the date/time of first dose of study drug and within 30 days after the last dose of study drug (see section 4.3 for detailed definition of "on-treatment").

In addition, the number and percentage of participants with at least one post-treatment vital sign measurement meeting any of these criteria will be summarized:

- Systolic Blood Pressure: <90 mmHg, >140 mmHg, >160 mmHg
- Diastolic Blood Pressure: <50 mmHg, >90 mmHg, >100 mmHg
- Pulse Rate: <60 bpm, >100 bpm
- Body Weight: decrease of  $\geq$ 7% from baseline and increase of  $\geq$ 7% from baseline
- Temperature: >38.0 °C, <36.0 °C

The number and percent of subjects meeting these criteria will be summarized for the Randomization and Extension Phase, separately as well as the overall BHV-4157 treated exposure. A subject listing will provide for each vital sign measure abnormality criteria listing any subject meeting the criteria with a complete list of all of their values that particular vital sign measure with the specific assessments that meet the criteria indicated.

The criteria summarized for the Randomization Phase will also be repeated for Treated subjects completing (or discontinuing) double-blind treatment prior to versus on or after start of COVID-19 pandemic crisis (March 13, 2020).

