#### 4.10.8 Sheehan-Suicidality Tracking Scale (S-STS)

The S-STS is a prospective, self-reported rating scale that contains 16 questions to track both treatment-emergent suicidal ideation and behaviors. In the event the participant is unavailable, the S-STS clinician-administered rating scale with 6 yes/no questions will be completed.

Self-reported S-STS scores are calculated as follows:

- Ideation subscale score: Sum of scores (0-4) for Questions 2-11
- Behavior subscale score: Sum of scores (0 4) for Questions 1a, (highest of 12 or any row of 16), (highest of 14 or any row of 15), 17, and 20 based on the scoring used for the 2017 version of scale used in this study. In addition, a Behavior subscale score based on the 2019 version of the scoring will also be calculated where the score for a 'Yes' item 20 is 56 and the scores for 18, 19, 21 and 22 are used from the prior visit if applicable.
- Total score: Sum of the ideation and behavior subscale scores. A Total score will be calculated based on both 2017 version and 2019 version

The self-reported S-STS ideation subscale, behavior subscale, and total score will be summarized as the change from baseline (i.e., <-1, -1, no change, 1, >1) at each visit and at Maximum score in the Randomization and Extension Phases, presented separately. Both

versions of the Total score will be summarized. All S-STS assessments will be included in summaries regardless of being completed at study site or remote.

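### SAP Table 3 has no follow-up row, so an off-drug visit within 30 days of the last dose replaces the true Week 48 vital signs, ECG and S-STS values in by-visit safety summaries

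*SAP*

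**What the plan says.** SAP 4.3.8 places Tables 1 to 3 under the heading "On-Treatment Analysis Windows" and explains that "analysis windows will be continuous to include all data". Table 3 covers S-STS, vital signs, laboratory tests, PK and ECG in the double-blind phase. Its final row is Week 48, target Day 336, interval Day 323-420. No row exists for Week 52 or any other follow-up. Below the table stands the rule for repeats: "If a participant has more than one record within an analysis window, the latest record within the window will be used in the analysis".

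SAP 4.4, in the item beginning "On-Treatment in Randomization Phase (Safety Assessments): except where indicated", ends the on-treatment period at the first extension dose or "up to the last day of Randomization Phase study drug + 30 days, whichever comes first". SAP 4.10.5 (vital signs) and 4.10.6 (ECG) repeat the limit: "within 30 days after the last dose of study drug". SAP 4.10.8 summarises S-STS change "at each visit and at Maximum score in the Randomization and Extension Phases" and does not repeat it. Laboratory tests have their own repeat rule in 4.10.3: an abnormal value takes precedence, and otherwise "the worst measurement in the analysis" visit interval is shown.

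Protocol 8.1.10 schedules vital signs, weight, laboratory tests, ECG and S-STS at Week 52 for participants not going into the extension. Protocol section 2 describes this as a post-treatment period and tells direct extension entrants to skip the visit.

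**The concern.** Read together, these rules give the Week 48 row a value that was not taken at Week 48. A participant who attends Week 48 on drug and Week 52 off drug has two records in one window, and the later one is kept. A direct extension entrant has only the Week 48 record. One by-visit row therefore mixes end-of-treatment readings with readings taken about three to four weeks after the last dose, divided by whether the participant moved straight into the extension.

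What is at stake is the description of the last treatment visit for blood pressure, pulse, weight, ECG intervals and S-STS change. For S-STS the time frame shifts as well: protocol 9.4 sets the recall period as the time since the last visit, so a Week 52 score covers the off-drug interval.

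**Working it through.** **1. The plan's own window.** Target: 48 × 7 = Day 336. Lower bound: midpoint of the Week 44 and Week 48 targets plus one, (308 + 336)/2 + 1 = 323. Upper bound: the 60-week COVID maximum in protocol 8.1.9, 60 × 7 = 420. All agree with Table 3, so the upper bound is intended and is not itself the error.

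**2. Where Week 52 falls.** The protocol allows two anchors.
- Anchored to the Week 48 visit (8.1.9, return after 28 ± 7 days): gap 21-35 days. From an on-time Week 48 visit (Day 329-343), follow-up lies on Day 329 + 21 = 350 to 343 + 35 = 378.
- Anchored to baseline (heading of 8.1.10 and the visit schedule, Week 52 ± 7 days): 52 × 7 = 364, so Day 357-371.

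Both ranges lie wholly inside Day 323-420. With Week 48 on Day 336 the two anchors coincide.

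**3. The 30-day limit.** Let *g* be the gap from the Week 48 visit to Week 52 and *k* the days from the last dose to the Week 48 visit. The follow-up counts as on-treatment, and is the latest record in the window, if *g* + *k* ≤ 30. At the nominal *g* = 28:

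| *k* | *g* + *k* | Week 48 value |
|---|---|---|
| 0 | 28 | replaced |
| 1 | 29 | replaced |
| 2 | 30 | replaced |
| 3 | 31 | kept |

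With *k* = 0, gaps up to 30 days replace Week 48, and gaps of 31-35 days do not.

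**4. S-STS.** If 4.4 governs 4.10.8, step 3 applies unchanged. If it does not, follow-ups at 31-35 days also replace Week 48.

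**5. Laboratory tests.** The latest-record rule gives way to 4.10.3. A Week 52 result within 30 days of the last dose joins the Week 48 interval and is shown there if the abnormal-or-worst rule selects it.

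**6. Extension visits after a dosing gap.** The abbreviated dispensing visit (off drug for at most 4 weeks) collects vital signs and S-STS. The full extension baseline visit also collects weight, ECG and laboratory tests, but it follows a break of about 4 weeks or more, so it meets the limit only at about 28 to 30 days. Section 4.4 counts records up to the first extension dosing day, so both visits can supply the latest record in the Week 48 window.

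**7. Delayed Week 48.** A 28-day follow-up stays in the window only if Week 48 took place by Day 420 − 28 = 392. After that it passes Day 420 and belongs to no row.

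**8. Table 5.** The extension Week 48 row is Day 295-420. The visit two weeks after the last extension dose (14 ± 7 days) collects vital signs and S-STS. With extension Week 48 and the last dose on Day 336 it falls on Day 343-357, 7-21 days off drug, inside both limits. The latest-record rule is printed before Table 5. If it applies there too, the same replacement follows.

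**The case against.** The best defence is that this is design. The SAP deliberately allows 30 days for safety against 3 days for efficacy. It bins by study day, with rows for Weeks 16, 20, 28, 32, 40 and 44, when no visit is scheduled, and it nowhere promises that the Week 48 row describes the last treatment visit. This stands in part: admitting off-drug data to on-treatment safety breaks no SAP rule. It does not explain discarding a valid end-of-treatment reading and printing a later one under the Week 48 label.

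One might answer that by-visit means the nominal visit. But Table 3 sets windows for exactly these parameters, and no passage prefers the nominal Week 48 record or excludes Week 52.

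The timing assumptions are a fair target. Protocol 6.5 ties the end of dosing to the end-of-treatment visit without fixing the last-dose day. Protocol 8.3 asks morning attenders to hold the dose until after the PK sample, which postpones it and does not show that it is omitted. If Week 52 is anchored to baseline, a Week 48 visit on Day 329-343 gives gaps of 357 − 343 = 14 to 371 − 329 = 42 days. A reader might note that, with *k* = 0, 10 of the 15 gap days from 21 to 35 lead to replacement, and infer that about two thirds of follow-up visits are affected. The documents do not support that. These are calendar days, not participants, and the count changes with the anchor and the last-dose date.

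A reader might also infer a distorted drug-placebo comparison. The same derivation applies to both arms, and the documents give neither Week 52 attendance by arm nor how fast any effect reverses off drug. No direction or size of bias can be derived.

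**Conclusion.** The point holds as a minor error in the rules as written. An off-drug visit within 30 days of the last dose takes the place of the true Week 48 vital signs and weight, S-STS and, where one is recorded, ECG. At the nominal schedule this is the expected result for *k* = 0 to 2, not a rare case. Week 52 laboratory values enter the Week 48 row by a different route.

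The reach is limited to descriptive by-visit rows. At-least-one counts for vital signs and QTcF, highest laboratory grade and maximum S-STS do not depend on which record fills the row. The co-primary analyses do not use Table 3.

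The conclusion assumes that Table 3 is programmed literally and that the last dose falls on the Week 48 visit day or up to two days before. For S-STS, the extent depends on whether 4.4 governs 4.10.8. How many participants are affected cannot be determined from the documents.

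**What to change.** 1. In the Week 48 row of Table 3, use the nominal Week 48 visit record when one exists on Day 323-420. Otherwise use the latest record in that window, excluding the nominal Week 52 visit and any extension dispensing or baseline visit held after a dosing gap. This keeps COVID-delayed Week 48 visits, and the Day 323 bound still keeps out earlier early-termination visits.
2. Add a Week 52 / follow-up row that takes the nominal Week 52 visit whatever its study day. State that this row is exempt from the 30-day limit in 4.10.5 and 4.10.6. Without the exemption, vital signs and ECGs taken beyond 30 days would drop out of the new row.
3. Exclude the same off-drug visits from the Week 48 by-visit laboratory row.
4. Apply the same rule to Table 5 for the visit two weeks after the last extension dose.

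Leave the 30-day definition in 4.4 unchanged for at-least-one and worst-value summaries. The cost is one table row, a few sentences and a small change to the visit derivation. No new data are needed.

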# Table 4:Analysis Windows for All efficacy assessments and the VolumetricMRI, in the 48 week Extension Phase

Evaluation	Protocol-Specified Day	Analysis-Specified Interval
Extension Phase		
Week 24	Day 168	Day 2-252
Week 48	Day 336	Day 253-420

Note: Baseline assessment will be defined as the last available assessment on or before first day of extension phase study drug as long as it is within 28 days of the first day of extension phase medication. Days based on days from first day of extension phase study drug.

Table 5:	Analysis Windows for Safety Parameters: Sheehan Suicidal
	Tracking, Vital Signs, Lab Assessments, and ECG in the 48 week
	Extension Phase

Evaluation	Protocol-Specified Day	Analysis-Specified Interval
Extension Phase		
Week 4	Day 28	Day 2-42
Week 8	Day 56	Day 43-70
Week 12	Day 84	Day 71-126
Week 24	Day 168	Day 127-210
Week 36	Day 252	Day 211-294
Week 48	Day 336	Day 295-420

Note: Baseline assessment will be defined as the last available assessment on or before first day of extension phase study drug as long as it is within 28 days of the first day of extension phase medication. Days based on days from first day of extension phase study drug.

#### 4.4 Analysis Periods and Study Phases

Analysis periods and study phases are defined as follows:

- Screening Phase: will include all assessments on or before the first day of study drug.
- On-Treatment in Randomization Phase (Safety Assessments): except where indicated, "ontreatment" in the Randomization Phase will include all assessments after first day of study drug and up to the first day of dosing of the Open Label Extension Phase study drug (for subjects entering extension) or up to the last day of Randomization Phase study drug + 30 days, whichever comes first. For AEs, "on-treatment" in the Randomization Phase will include first day of dosing of the Randomization Phase study drug up to the last day of Randomization Phase study drug + 30 days for those not going into the Extension Phase or up to the day before the first day of dosing of Extension Phase medication for those subjects who do.
- On-Treatment in Randomization Phase (Efficacy Assessments): except where indicated, "on-treatment" in the Randomization Phase will include all assessments after first day of study drug and up to the first day of dosing of the Open Label Extension Phase study drug (for subjects entering extension) or up to the last day of Randomization Phase study drug + 3 days, whichever comes first.
- On-Treatment in Open Label Extension Phase (Safety Assessments): except where indicated, "on-treatment" in the Open Label Extension Phase will include all assessments after first day of open label study drug and up to the last day of Open Label Extension Phase study drug + 30 days. For AEs, "on-treatment" in the Open Label Extension Phase will include first day of dosing of the Open Label Extension Phase study drug up to the last day of Open Label Extension Phase study drug up to the last day of Open Label Extension Phase study drug + 30 days.
- On-Treatment in Open Label Extension Phase (Efficacy Assessments): will include all efficacy assessments after the first day of dosing of OL Extension Phase study drug to the

last day of study drug +3 days. Baseline for the extension will be the last available assessment on or before the first day of dosing of OL Extension Phase medication.

• On-Treatment in Study (Safety Assessments): except where indicated, "on-treatment" for any Troriluzole treatment (combined Randomization Phase and Extension Phase) will include all assessments after first day of Troriluzole and up to the last day of Troriluzole treatment + 30 days. For AE summaries for any Troriluzole treatment (combined Randomization Phase and Extension Phase), On-treatment (Troriluzole) will include AEs with start date on or after first day of dosing with Troriluzole up to last day of dosing with Troriluzole + 30 days.

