 - o For participants who will have been off of the study drug for less than or equal to 4 weeks, the subject should come into the investigative site for an Abbreviated Drug Dispensation Visit (also "Abbreviated OLE Baseline Visit"), at which time any major medical or medications changes will be reviewed prior to dispensing riluzoleIn this case, most procedures from the Week 48 visit will also serve as the Open-Label Extension phase Baseline visit, as outlined in Table 3 (Schedule of Assessments/Time & Events- Extension Phase). Thereafter, participants will undergo visits at Week 4, Week 8, Week 12, and then every 12 weeks of the Extension Phase.

For participants who have been off the study drug for greater than 4 weeks, these participants should be re-assessed and re-consented by the PI during an Open-Label Extension Baseline Visit. From the date that the Open-Label Extension is open for recruitment at the study site, these participants that completed the study prior will have up to approximately 12 weeks to complete the Open-Label Extension Baseline Visit. Thereafter, participants will undergo visits at Week 4, Week 8, Week 12, and then every 12 weeks of the Open-Label Extension phase as outlined in Table 3 (Schedule of Assessments/Time & Events- Extension Phase). All previous completers of the double-blind phase will have a 12-week window of opportunity to baseline into the OLE, regardless of their date of double-blind phase completion. In the event sites open for Open-Label recruitment, then close due to COVID-19 before enrolling all prior completers, exceptions to the 12-week window will be considered on a case-by-case basis following discussion with the Sponsor Medical Monitor:

- As with the double-blind phase, certain provisions may be implemented, in order to minimize potential hazards to study participants due to COVID-19. These provisions may allow alternatives to in-person study visits and include but are not limited to the following: conducting remote visits via phone/telemedicine video, focusing on safety assessments during remote visits, performing safety labs via local labs or professional in home phlebotomy vendors, and shipping study medication to study participants if needed. Any potential issues should be discussed with the Sponsor and will be addressed on an individualized basis.

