11 DEFINITION OF ADVERSE EVENTS

An adverse event (AE) or adverse experience is any untoward medical occurrence in a study participant who is administered a medicinal product, that does not necessarily have a causal relationship with the study treatment, and that occurs after informed consent is signed and up to 30 days after the study drug has been discontinued. An AE can therefore be any unfavorable and unintended sign, symptom, or disease temporally associated with the use of a medicinal product, whether or not considered related to the medicinal product. Pre-existing conditions, which increase in frequency or severity or worsen in nature during, or as a consequence of, use of a drug in human clinical trials, will also be considered adverse experiences. Adverse events may also include pre- or post- treatment complications that occur as a result of protocol-mandated procedures (e.g. invasive procedures such as biopsies).

An AE does not include:

- Medical or surgical procedures (e.g., surgery, endoscopy, tooth extraction, transfusion).
 The condition that leads to the procedure is the AE.
- Situations where an untoward medical occurrence has not occurred (e.g., hospitalization for elective surgery, social and/or convenience admissions).
- Worsening of symptoms associated with expected decline in Alzheimer's disease is not considered an adverse event in this study.
- Overdose of either study drug or concomitant medication without any signs or symptoms unless the participant is hospitalized for observation. Overdoses should be reported as outlined in Section 11.4.

A treatment emergent adverse event (TEAE) is defined as any AE that developed, worsened, or became serious after first dose of study drug and prior to 30 days after the last dose of study drug.

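### For participants who enter the extension after a break, the double-blind AE window in SAP 4.4 has no 30-day limit, so late off-drug events can count as on-treatment

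*SAP*

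**What the plan says.** SAP 4.4 gives two rules for where the Randomization Phase safety window ends.

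- **Safety assessments in general:** the window closes at the first open-label dose "or up to the last day of Randomization Phase study drug + 30 days, whichever comes first".
- **AEs:** the rule depends on later entry into the extension. For some participants it runs "up to the last day of Randomization Phase study drug + 30 days for those not going into the Extension Phase"; for entrants it continues "or up to the day before the first day of dosing of Extension Phase medication for those subjects who do". The entrants' branch has no 30-day limit.

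SAP 4.10.2 refers to 4.4 for the on-treatment definition of TEAEs. It tabulates the number and percentage of participants with events by treatment group, separately for each phase.

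SAP 4.10.3 first defines an on-treatment lab abnormality as one with an "assessment date after the date/time of first dose of study drug and within 30 days after the last dose of study drug". The next sentence ends the Randomization Phase window for treatment-emergent abnormalities at "1) the first day of the Extension Phase or 2) if the subject did not continue into the Extension Phase, 30 days after" dosing stops.

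Protocol section 11 defines a TEAE as an event that arises, worsens or becomes serious "after first dose of study drug and prior to 30 days after the last dose of study drug". Protocol 11.1 and the AE footnote to Appendix I Table 1 stop AE recording 30 days after study drug is discontinued.

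Protocol section 2, repeated in 8.1.12, admits prior completers who have been off drug for more than 4 weeks. They "will have a 12-week window of opportunity to baseline into the OLE, regardless of their date of double-blind phase completion", with case-by-case exceptions where a site closed again because of COVID-19.

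**The concern.** The entrants' branch suits a participant who moves straight from the Week 48 visit to open-label drug, because the gap is then close to zero. It does not suit someone who finished before the extension opened at the site and returned weeks or months later. For that person, events well after the last double-blind dose are labelled as double-blind on-treatment events.

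The longer window depends on something that happens after randomisation. Participants who terminated early or stopped drug cannot enter the extension (Protocol 2 and 8.1.12), so only completers who choose to continue can have it. The AE tables are percentages of participants with no exposure adjustment. The active-versus-placebo safety comparison would then mix on-drug events with off-drug background events, over windows whose length depends on a later choice.

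**Working it through.** The plan states no figure on this point, so the check compares the definitions and then does the date arithmetic.

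**1. The end dates side by side**

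| Item | Enters extension | Does not enter | Source |
|---|---|---|---|
| General safety assessments | earlier of first open-label dose and last dose + 30 days | last dose + 30 days | SAP 4.4 |
| AEs | day before first open-label dose, no limit | last dose + 30 days | SAP 4.4 |
| Labs, on-treatment | last dose + 30 days | last dose + 30 days | SAP 4.10.3 |
| Labs, treatment-emergent | first day of extension, no limit | last dose + 30 days | SAP 4.10.3 |

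The summaries of vital signs (SAP 4.10.5) and ECG (SAP 4.10.6) keep the 30 days.

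**2. Can the gap exceed 30 days?** Let *d* be the days off drug when the site opens for the extension. Prior completers then have about 12 weeks (84 days) to enter, so the latest ordinary entry gives

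gap = *d* + 84, and excess over the limit = gap − 30.

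The documents give no site-opening or completion dates. The values of *d* below are assumptions that show the range.

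| *d* (assumed) | Maximum gap | Excess over 30 days |
|---|---|---|
| 1 day | 85 | 55 |
| 28 days | 112 | 82 |
| 56 days | 140 | 110 |
| 84 days | 168 | 138 |
| 182 days | 266 | 236 |

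One lower bound needs no assumed *d*. The extension came in with protocol version 05 on 24 April 2020, and SAP 4.7 plans a summary of participants who completed or discontinued before 13 March 2020. From 12 March to 24 April 2020 is 43 days. Taking last dose as the completion date, anyone who completed by 12 March and later enters has been off drug at least 43 days, at least 13 beyond the limit. If the site opened on 24 April itself (assumed), the gap could reach 43 + 84 = 127 days, an excess of 97.

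**3. Can gap events reach the database?** Some can. The extension baseline visit is required after a break of 4 weeks or more, and Protocol Appendix I Table 3 schedules AE assessment and labs there. A new consent is signed, and Protocol 11.1 records AEs from consent. Protocol 11.3 also asks for SAEs after the 30 days when they are believed related to study drug or study procedures. No visit is scheduled between Week 52 and the extension baseline, so the gap is otherwise unobserved.

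**4. Where are they counted?** An AE starting on, say, day 60 of a 112-day gap comes before the first open-label dose. The AE sentence in SAP 4.4 therefore places it in the Randomization Phase. The same event on the same day in a non-entrant would be excluded.

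**5. Labs.** The grade and shift tables in SAP 4.10.3 use the on-treatment term, which has the 30-day limit. The unlimited treatment-emergent sentence contradicts the sentence before it, and no table described there clearly relies on it.

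**6. After the fix.** Off-drug time in the AE window is at most 30 days for everyone. The days removed at the maximum gap are those in the excess column above.

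**The case against.** The strongest reply has five parts.

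- **The exception is deliberate.** The general rule in SAP 4.4 allows for exceptions, and assigning a between-phase event to the preceding phase is a recognisable convention. The protocol's TEAE definition is also not phase-specific; for an entrant, the last dose could be read as the last open-label dose. This stands in part: the conflict with the TEAE definition depends on reading it for the double-blind phase. But nothing in the protocol assigns a gap event to double-blind treatment, and Protocol 11.1 ends AE recording 30 days after drug is stopped.
- **SAP 4.5.2 keeps extension data out of the primary analysis.** This does not help, because the AE sentence itself places gap events in the Randomization Phase.
- **Few participants are affected.** Once a site is open, completers must roll over directly (Protocol 8.1.12), and their AE window is shorter than last dose + 30 days. This stands. Only prior completers with breaks over 30 days matter, and their number is not given.
- **The gap is not observed time at risk.** This stands. A reader might infer a percentage increase in follow-up by setting 48 weeks plus an assumed gap against 48 weeks + 30 days (52.3 weeks). The documents do not support that: the gap lengths are unknown, recording in the gap is incomplete, and non-entrants can have up to 60 weeks of treatment + 30 days, which is 450 days or 64.3 weeks (Protocol 8.1.9).
- **No arm bias is shown.** This also stands. The rule is the same in both arms and SAP 4.10.2 plans no formal test of AE rates. A reader might infer a direction from the completion rates in the earlier ataxia trial (64/71 on drug, 68/70 on placebo; Protocol 1.7.1.1). That was an 8-week trial at 140 mg in another disease, and it says nothing about entry into this extension.

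**Conclusion.** The AE definition is wrong as written for one subset: prior completers who enter the extension more than 30 days after their last double-blind dose. For them, recorded events beyond 30 days count as double-blind on-treatment events. The same events in non-entrants do not, and other safety assessments in SAP 4.4 follow the 30-day limit for everyone.

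The excess window is 55 to 138 days at the latest ordinary entry if the participant had been off drug between 1 day and 12 weeks when the site opened, and longer for earlier completers. These are calendar lengths under assumed dates; they do not measure added events. Neither the change in event counts nor any difference between arms can be derived from the documents.

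A reader might also infer that the lab tables lose the 30-day limit. The documents do not show that. The lab point is an inconsistency between two adjacent sentences in SAP 4.10.3.

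**What to change.** - In SAP 4.4, end the Randomization Phase AE window at the earlier of last double-blind dose + 30 days and the day before the first open-label dose.
- In SAP 4.10.3, give the treatment-emergent lab sentence the same end rule, so that it agrees with the on-treatment sentence before it.
- List AEs and lab abnormalities that fall after the 30 days and before the first open-label dose separately, as off-treatment, so that no recorded event is lost.

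The cost is one sentence in each of the two sections and one added listing. No new data are needed. The change is best made before the double-blind data are unblinded, since choosing the window afterwards would be open to challenge.
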